3 STUDY DESIGN

3.1 Characteristics

We propose a 2-arm, 90 patient (45 per cohort) trial in patients who will be undergoing mastectomy with immediate tissue-expander reconstruction to determine whether treatment with zafirlukast (20mg PO BID) can reduce or prevent the development of capsular contracture. All patients undergoing mastectomy with immediate tissue-expander placement will be approached

in clinic at the time of their initial consultation with the plastic surgeon and enrolled in the trial at this point. Approximately 60 women undergo mastectomy with tissue-expander reconstruction at our institution per year, thus enrollment will occur over a two-year period.

Patients will be block randomized 1:1 into two cohorts: treatment with zafirlukast and the standard of care, or standard of care alone. Patients will begin treatment with zafirlukast on post-operative day one (+/- 5 days) following placement of tissue expander(s) after the participant is determined safe from a surgical recovery standpoint. They will be continued on the standard dosing (20mg PO twice per day) of zafirlukast through expander fill. Last dose of Zafirlukast will be administered the day prior to expander implant exchange procedure. Patients will be seen every 1 to 2 weeks for expander fill, and will be assessed clinically (refer to section 6.2 for research visits). The treating physician will determine the frequency of visits based on each patient's expander need.

During expander-implant exchange, three representative sections of the expander capsule will be collected: medial, lateral and anterior capsule specimens. These specimens will be bisected; half will be sent to pathology and half will be collected by the [name] lab. Gross and microscopic determination of capsule thickness will be performed by the pathology department. The [name] lab will fix and stain the tissues to look for the presence of collagen, level of fibrosis, and number of myofibroblasts. Fibrosis level and collagen presence will be determined by performing immunohistochemistry with a Trichrome stain of the tissues, as well as Western blot analysis with Collagen-1. Myofibroblasts will be detected using immunohistochemistry with commercially available antibodies.

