Period/ Procedure	Screening ⁹	Treatment period (+/- 1 week)				Expander- implant exchange	End of Treatment	Follow up visits ⁵
Study Day/Visit Day	Days -28 to Day 1	Mastectomy and Tissue- expander placement (week 0)	Day 15-21 (wk 2)	Day 29-35 (wk 5)	Day 71-77 (wk 11)	Day 113-119 (wk 17) ⁸		
Informed Consent	x							
Baseline Conditions ¹	x							
Tissue Specimen Collection						x		
Zafirlukast ⁶		x						
Medical History	x						x	
Vital Signs	x		x	x	x	x	x	x
Physical Exam	x		x	x	x	x	x	x
Con-med and AE review ⁷		x					x	
CBC w/diff ²	x		x	x	x	x	x	
Chemistry ³	x		x	x	x	x	x	
Liver Function Tests ⁴	x			x			x	
Pregnancy Test (HCG)	x							

1. Baseline conditions assessment per DSMC policy.
2. Including CBC with differential and platelet count.
3. Including creatinine, fasting glucose, potassium, sodium, chloride, bicarbonate.
4. Including alkaline phosphatase, ALT/AST, total bilirubin. For Cohort A only on week 5 and EOT. Alkaline phosphatase is not required for screening.
5. Patients are followed for two years after implant reconstruction. After implant exchange we will see patients every 2 weeks for the first month, every month for the subsequent 4 months, and, every 6 months for the remainder of the two years. For those patients are removed from treatment, they will be followed as per our standard of care which is monthly for the first six months and then every six months for a total of two years.
6. 20mg PO twice per day from Day 1 to Treatment Termination for Cohort A only. Treatment may continue until tissue expansion is complete. Zafirlukast should be stopped prior to expander implant exchange.
7. Con-med and AE review begins 28 days prior to treatment and continues 30 days after treatment termination.
8. As needed .
9. Screening procedures must be completed prior to mastectomy and tissue-expander placement.

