9.1 Analyses Plans

This is an intention to treat analysis. All patients who were randomized will be evaluated.

Data will be summarized using descriptive statistics by study cohorts. For continuous variables, descriptive statistics will include the number of non-missing values, mean, standard deviation, median, minimum and maximum. For categorical variables, descriptive statistics will include counts and percentages per category by study cohorts.

Primary analysis:

The primary objective of the trial is to determine the capsule contracture between the two study cohorts and the primary efficacy outcome in this trial is capsule thickness at the time of expander-implant exchange. Capsule thickness will be determined by averaging thickness from three separate specimens per patient. The capsule thickness will be analyzed by study cohorts, and t-tests and descriptive statistics with mean, standard deviation and 95% confidence intervals will be used for significance. Missing data will not be imputed. An alpha level of 0.05 will be considered significant for the primary endpoint. For exploratory analysis, the primary endpoint of capsule thickness will be presented as mean \pm SEM and evaluated using analysis of variance (ANOVA) with factors including study cohort, radiotherapy and length of drug treatment.

Secondary Analysis:

For secondary objectives of the trial, we will determine the level of fibrosis and presence of collagen from the biopsy specimens. The level of fibrosis and the presence of collagen will be analyzed descriptively as continuous levels and as ordinal levels with mean, standard deviation and 95% confidence intervals. The difference in the level of fibrosis and relative presence of collagen between study cohorts will be compared using t-tests for significance.

Similar statistical methods will also be employed to analyze the capsule tissue that is removed at the time of expander-implant exchange to determine the level and presence of collagen, fibroblasts and myofibroblasts.

Confounding Factors:

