In addition to primary and secondary analysis, we will also determine if there are other confounding factors such as variables in time and length treated with zafirlukast and radiation therapy by using ANOVA models on capsule thickness. Univariate analysis will be done on capsule thickness with all potential factors and selected variables of interest deemed significant will be further analyzed for interaction effect. Capsule thickness will be reported per subgroup of patients to account for time and radiation variables.

Other analysis:

An interim analysis is planned at 1 year to assess treatment efficacy in the treatment group compared to standard of care group.

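### The exploratory ANOVA puts length of zafirlukast treatment, which only Cohort A has, beside study cohort with no coding or test order, so its cohort line need not be the randomised contrast

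*Combined protocol and SAP*

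**What the plan says.** The primary analysis in Section 9.1 is an unadjusted t-test of mean capsule thickness between cohorts. The same paragraph adds a further model, introduced by "For exploratory analysis, the primary endpoint of capsule thickness will be presented as mean" and "evaluated using analysis of variance (ANOVA) with factors including study cohort, radiotherapy and length of drug treatment".

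Under Confounding Factors, Section 9.1 returns to the subject and looks for "confounding factors such as variables in time and length treated with zafirlukast and radiation therapy by using ANOVA models on capsule thickness". A univariate screen follows, after which "selected variables of interest deemed significant will be further analyzed for interaction effect". The closing sentence is "Capsule thickness will be reported per subgroup of patients to account for time and radiation variables".

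Section 3.1 defines the arms as "treatment with zafirlukast and the standard of care, or standard of care alone", with no placebo. Footnote 6 of Table 6 gives the drug as "20mg PO twice per day from Day 1 to Treatment Termination for Cohort A only". Under Section 6.2, patients are randomised on the day of surgery, the surgeon and patient learn the cohort straight afterwards, and dosing starts after surgery and runs until expansion is complete.

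Nowhere does the plan state the value of drug length for Cohort B, its scale (continuous or banded), any centring, or the type of sums of squares.

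**The concern.** A confounder of a randomised comparison would have to precede allocation. Length of drug treatment follows allocation, is a dimension of the treatment itself, and does not exist in the control arm. In one model with cohort, it nearly duplicates cohort, and the meaning of the cohort line then rests on a coding that nobody has fixed. The trial is open-label, so the coding could be chosen with results in view.

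This is the plan's only adjusted analysis of the primary endpoint. A reader will naturally take its cohort line as the treatment effect after allowance for confounding. An effective drug could show a cohort effect near zero there. Drug length could also be reported as a significant confounder when it merely marks who received the drug.

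**Working it through.** **Inputs from Section 9.0.** Means 2.4 and 1.2 mm (difference 1.2 mm), SD 2 mm, two-sided 5% t-test. The section gives both 41 and 45 per arm, so both are used.

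**The plan's own figure.** With 45 evaluable per arm, the unadjusted SE is 2 × √(2/45) = 0.42 mm, and noncentral-t power is 80.4%, which agrees with the stated >80%. With 41 per arm, the SE is 2 × √(2/41) = 0.44 mm and power is 76.5%.

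**Assumed, because the documents are silent.** Mean drug length m = 11 to 24 weeks and SD s = 3 to 8 weeks in Cohort A. Week 17 is the last treatment-period visit in Table 6, but it is marked as needed, so a mean of 17 weeks is only illustrative. The fits below omit radiotherapy.

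**Step 1: what each coding does to the cohort line.**

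| Handling of length | Cohort line |
|---|---|
| Three bands in A, 'none' in B | Design has 5 columns and rank 4; no separate cohort test once all bands are in |
| Missing in B, not imputed | 41 of 82 patients remain; cohort is constant (rank 2 of 3) |
| Continuous, 0 in B, partial test | Effect extrapolated to zero weeks of drug |
| Centred within A, 0 in B | Equals the unadjusted difference |
| Cohort tested first, sequentially | Tests the unadjusted difference |

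A cohort × length interaction cannot be fitted (rank 3 of 4). Length × radiotherapy can (rank 5 of 5).

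**Step 2: zero coding, point estimate.** Least squares gives

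cohort coefficient = (mean A − mean B) − (slope on length within A) × (mean length in A).

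- Benefit proportional to length, reaching −1.2 mm at 17 weeks: slope = −1.2/17 = −0.07 mm/week, so the coefficient is −1.2 + 1.2 = 0. Simulated averages at 41 per arm: −0.04 to 0.07 mm.
- Full 1.2 mm benefit whatever the duration, with capsules thickening by an assumed 0.05 mm/week in both arms: −1.2 − 0.05m, which is −1.75, −2.05 and −2.40 mm at m = 11, 17 and 24.

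In the same fits, the contrast at mean duration equals the unadjusted difference, −1.18 to −1.22 mm.

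**Step 3: zero coding, precision.** SE = 2 × √(2/n) × √(1 + (m/s)²/2). For m = 17, s = 4, n = 41, this is 0.442 × 3.17 = 1.40 mm. Simulation (2,000 trials per cell) gives slightly more, because s varies from trial to trial:

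| m, s (weeks) | SE, 41 per arm (mm) | SE, 45 per arm (mm) |
|---|---|---|
| 11, 3 | 1.26 | 1.20 |
| 11, 4 | 0.99 | 0.94 |
| 17, 3 | 1.88 | 1.78 |
| 17, 4 | 1.43 | 1.37 |
| 17, 6 | 1.02 | 0.97 |
| 17, 8 | 0.83 | 0.79 |
| 24, 4 | 1.98 | 1.89 |
| 24, 8 | 1.06 | 1.01 |

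That is 1.9 to 4.5 times the SE of the centred coding.

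**Step 4: the univariate screen across both arms, m = 17, s = 3 to 8.** If the drug has its full 1.2 mm effect regardless of duration, length is flagged in 61–74% of trials at 41 per arm and 65–78% at 45. If the drug does nothing, it is flagged in about 5%.

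**The case against.** The strongest reply is that the model is labelled exploratory. The t-test, the intention-to-treat rule and the 0.05 level stand apart from it, and no decision rests on it. That is true and limits the seriousness.

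Second, cohort is the first factor listed, and a sequential ANOVA in that order keeps the unadjusted contrast. Also true, but the plan does not say the tests are sequential, and a partial test gives a different answer.

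Third, the consequences in Step 1 are not inevitable. With banded length, dropping one band leaves a cohort coefficient that can be estimated; it then compares the reference band with control, which is still not the randomised contrast. The sentence "Missing data will not be imputed" belongs to the primary-analysis paragraph, so losing all controls is a possible reading and not the likeliest one.

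Fourth, the Confounding Factors paragraph does not name cohort as a factor, and its screen could be run within Cohort A. Its time variable may already mean time to exchange. Both readings are open, and the text should say which is meant.

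Fifth, the durations and the weekly trend are assumptions, and the flag rates in Step 4 largely restate the trial's power. They are not false positives for a drug effect. What would be wrong is calling the flagged variable a confounder. The rank results and the identity in Step 2 need no assumed durations.

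**Conclusion.** The concern holds. Section 9.1 lists cohort and drug length as factors of one model and calls drug length a confounder, although it exists in one arm only and is determined after randomisation. Under ordinary partial tests, the resulting cohort line is either not separately defined or refers to zero weeks of drug.

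The zero-coded coefficient is a valid quantity, but it is not the randomised difference. Centring or testing cohort first recovers that difference from the same data, so the fault lies in which coefficient is read. The size of the distortion, from about 0 mm to −2.40 mm against a true −1.2 mm, depends wholly on the assumed durations and trends.

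The damage is confined to the exploratory and confounder analyses; the primary t-test and the sample size are untouched. The plan should be changed, but its main conclusion is not at risk.

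**What to change.** In both paragraphs of Section 9.1:

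- Take length of drug treatment out of the two-arm ANOVA, the two-arm univariate screen and any interaction with cohort, and stop describing it as a confounder of the randomised comparison.
- Analyse it within Cohort A only, as a descriptive exposure-response slope with a 95% CI.
- Keep the unadjusted difference as the estimate of effect.
- Let any two-arm exploratory model use radiotherapy or time from expander placement to exchange, both of which are defined in both arms. Label it as adjusting for post-randomisation variables: Section 3.3.2 excludes prior chest wall radiation, and the cohort is known from the day of surgery.
- In the subgroup sentence, define time as time from placement to exchange, and report drug-length subgroups for Cohort A alone.

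If the sponsor prefers to keep length in the two-arm model, the minimum is to state that it is centred within Cohort A and set to 0 in Cohort B, or that cohort is tested first.

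The cost is wording: no new data, and no change to the primary test or sample size. The slope will be imprecise. With 41 patients, its 95% half-width is 2.02 × 2/(s × √40), about 0.21 mm/week at s = 3 and 0.08 at s = 8, against the 0.07 mm/week of Step 2. It is also a non-randomised comparison, because length reflects expansion time and early stopping (Sections 6.2 and 6.4), so it should be presented as descriptive.

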6.3 Randomization Procedures

This study is an open-label randomized trial; therefore the investigator and subject will know the treatment administered. Patients will be randomized by a study personnel other than the surgeon. The surgeon and patient will be notified of the patient's cohort immediately post-surgery. Two arms will be tested, with each independent assessment. Patients will be block randomized to either treatment with zafirlukast or the standard of care. Enrollment will continue until 90 patients (45 per cohort) have been enrolled.

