9.0 STATISTICAL CONSIDERATIONS AND EVALUATION OF RESULTS

Determination of sample size and accrual rate

Sample size calculated to be 82 (41 per arm) based on a two-tailed alpha of 0.05, with a beta of 0.18. With a possible 10% attrition rate, the sample size is increased to 90 (45 per arm). As approximately 60 patients undergo mastectomy with immediate tissue expander placement per year at Mt. Zion, it is expected that roughly 80% of these women will be enrolled in the study.

The determination of sample size is based on the assumption that treatment with the leukotriene inhibitor zafirlukast will decrease capsule thickness in women with tissue expanders at the time of implant exchange. Based on the reported results from literature review, a capsule thickness of >2.4mm would be considered undesirable and <1.2mm would be considered desirable. We assume the capsule thickness is <1.2mm under zafirlukast as the target efficacy of clinical importance for the study population and an efficacy of 50% reduction in capsule contracture between two cohorts would be considered clinically meaningful. Under the t-test with a 2-sided alpha of 5%, we will need 45 evaluable patients in each cohort to have >80% power to detect an

improvement in capsule thickness from average 2.4mm (sd 2mm) to average 1.2mm (sd 2mm). Specifically, the study hypothesis is defined as:

H0: $\mu_1 \geq \mu_0$ (The capsule thickness of the cohort A is greater than capsule thickness of the cohort B versus

H1: $\mu_1 < \mu_0$ (The capsule thickness of the cohort A is greater than capsule thickness of the cohort B.

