10.6 Case Report Forms (CRFs)

The Principal Investigator and/or his/her designee will prepare and maintain adequate and accurate participant case histories with observations and data pertinent to the study. Study specific Case Report Forms (CRFs) will document safety and treatment outcomes for safety monitoring and data analysis. All study data will be entered into OnCore® via standardized CRFs in accordance with the CTMS study calendar, using single data entry with a secure access account. The Clinical Research Coordinator (CRC) will complete the CRFs as soon as possible upon completion of the study visit; the Investigator will review and approve the completed CRFs.

The information collected on CRFs shall be identical to that appearing in original source documents. Source documents will be found in the patient's medical records maintained by UCSF personnel. All source documentation should be kept in separate research folders for each patient.

In accordance with federal regulations, the Investigator is responsible for the accuracy and authenticity of all clinical and laboratory data entered onto CRFs. The PI will approve all completed CRFs to attest that the information contained on the CRFs is true and accurate.

All source documentation and CTMS data will be available for review/monitoring by the UCSF DSMC and regulatory agencies.

The Principal Investigator will be responsible for ensuring the accurate capture of study data. At study completion, when the CRFs have been declared to be complete and accurate, the database will be locked. Any changes to the data entered into the CRFs after that time can only be made by joint written agreement among the Study Chair, the Trial Statistician, and the Protocol Project Manager.

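### The 1-year efficacy interim has no stated endpoint, time origin, permitted decision or significance level, so the plan does not secure its two-sided 5% error rate

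*Combined protocol and SAP*

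**What the plan says.** The full specification of the interim is one sentence in Section 9.1, under Other analysis: "An interim analysis is planned at 1 year to assess treatment efficacy in the treatment group compared to standard of care group". Its general purpose is therefore stated: a comparison of efficacy between the arms.

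Under Primary analysis, the same section sets the only significance rule in the plan: "An alpha level of 0.05 will be considered significant for the primary endpoint". Section 9.0 sizes the trial for a two-sided 5% t-test of 2.4 mm against 1.2 mm (SD 2 mm), with no mention of an interim.

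Other text bears on how the look might be used:

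- Section 6.3: "Enrollment will continue until 90 patients (45 per cohort) have been enrolled".
- Section 10.6: "At study completion, when the CRFs have been declared to be complete and accurate, the database will be locked".
- Appendix 1, Section 3.3: the only halt to enrollment or the study that it describes is for safety.
- Sections 8.6 and 10.7 and the rest of Appendix 1: adverse events, data review and audits, with no efficacy boundary.

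**The concern.** A planned efficacy comparison, followed by a final test that still has the whole 0.05, gives two chances of a false positive if both can lead to a claim. The plan leaves four things open that decide whether this happens: the interim endpoint, the origin of the year, the decision that may follow, and the threshold. A reader of the final report could not tell whether a p-value just under 0.05 carries its stated error rate. If the choice is made after the interim data have been seen, nobody can check it later.

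A second consequence is precision. An early look would rest on few patients, so a significant result at that point would have to show a difference larger than the one the trial was designed to detect.

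**Working it through.** **Inputs from the documents**

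- Two-sided alpha 0.05, difference 1.2 mm, SD 2 mm, 45 evaluable per arm (Section 9.0).
- Accrual: about 60 eligible women per year, and "it is expected that roughly 80% of these women will be enrolled in the study" (Section 9.0). This gives 0.8 × 60 = 48 per year, so 90 patients take 90/48 = 1.875 years, or 97.5 weeks.
- Attrition of 10% (Section 9.0). It applies equally to the interim and final counts, so it cancels in the information fraction.

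**Assumptions**

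- The year runs from first enrollment, and accrual is even.
- The lag from enrollment to exchange is 17 to 35 weeks. The documents give no fixed time. Table 6 lists a last treatment-period visit at "Day 113-119 (wk 17"), footnoted as needed, and enrollment precedes surgery, so 17 weeks is towards the short end.
- The interim tests capsule thickness.

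**Step 1. The plan's own figure.** The exact (noncentral t) power for 45 per arm is 80.4%, which agrees with the stated power above 80%. That calculation is for a single test.

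**Step 2. Information at the look.** Patients with the endpoint = 48 × (52 − lag)/52, and information fraction t = that number/90.

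**Step 3. Overall error.** Under no effect, the two test statistics are approximately bivariate normal with correlation √t. The error is P(|Z1| > 1.96 or |Z2| > 1.96).

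| Lag (weeks) | Patients past exchange | t | After 10% attrition | Overall error, 0.05 at both looks |
|---|---|---|---|---|
| 17 | 32.3 | 0.36 | 29.1 (about 14 per arm) | 8.8% |
| 26 | 24.0 | 0.27 | 21.6 (about 11 per arm) | 9.0% |
| 35 | 15.7 | 0.17 | 14.1 (about 7 per arm) | 9.3% |

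Simulated t-tests under no effect agree. With a final 40 per arm, the error is 9.1% for an interim at 11 per arm and 8.8% for one at 14 per arm.

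Later looks give less: 8.3% at t = 0.50, 7.1% at 0.80 and 6.0% at 0.95. At t = 1 the two analyses coincide and the error is 5%. The ceiling for two looks, reached only if they were independent, is 1 − 0.95² = 9.75%.

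**Step 4. Uses of the look that do not inflate the error.** If the look cannot support a claim, only the final test counts and the error is 5%. Suppose instead that the trial stops, without a claim, whenever the interim estimate favors control. By symmetry, half of the false positives are then lost, and the error is 0.05/2 = 2.5%.

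**Step 5. What an early significant result would show.** The smallest significant difference is t(0.975, 2n − 2) × 2 × √(2/n).

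- 14 per arm: 2.056 × 2 × 0.378 = 1.55 mm; power for 1.2 mm is 33%.
- 11 per arm: 2.086 × 2 × 0.426 = 1.78 mm; power 27%.
- 7 per arm: 2.179 × 2 × 0.535 = 2.33 mm; power 18%.

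Each threshold is above the 1.2 mm design difference.

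**Step 6. A split that controls the error.** With interim p < 0.001 and final p < 0.049, the overall error is 4.97% at t = 0.17, 4.96% at 0.27, 4.94% at 0.36 and 4.90% at 0.80. Testing at 0.049 instead of 0.05 lowers final-test power from 80.4% to 80.1% at 45 per arm. It falls from 76.0% to 75.7% at 40.5 per arm, that is, if 10% of the 45 are lost.

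**The case against.** The best defense is that the plan contains one confirmatory test. The 0.05 rule sits under Primary analysis and the interim under Other analysis. Section 6.3 directs that enrollment continue to 90, the database is locked at study completion, and the only stop described is for safety. On that reading the look is supplementary and the 5% level is intact.

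Much of this stands. The enrollment sentence and the safety-only stop lean clearly against stopping early for efficacy. A reader might infer that the trial will stop early on efficacy, or that the plan already breaches 5%; the documents support neither. They do not, however, bar an efficacy claim at one year while enrollment continues. A lock date governs data changes and does not restrict inference.

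Three further limits are fair:

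- A stop inflates the error only if it declares efficacy; a futility stop lowers it.
- If the look used another measure, none of the primary endpoint's alpha would be spent.
- If the year ran from last enrollment and every exchange had taken place by then, the look would coincide with the final analysis. The documents give no maximum time to exchange, so this cannot be assumed either way.

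Open-label treatment (Section 6.3: "This study is an open-label randomized trial; therefore the investigator and subject will know the treatment administered") might be read as making the excess worse. It has no bearing on the two-look calculation.

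**Conclusion.** The concern holds in conditional form. The omission is certain: endpoint, time origin, permitted decision and significance level are all missing for a planned efficacy comparison, beside a final test at the full 0.05. An excess arises only if the look tests capsule thickness at 0.05 and can support an efficacy claim, including a stop that declares efficacy. The overall error is then about 9% for a look one year after first enrollment, under the accrual and lag assumed above. It changes little across the lags tried, and it falls towards 5% as the look moves later. The 8.8 to 9.3% range describes that scenario; it does not bound every way the look might be used. Because the plan's only significance rule, applied at both looks, would nearly double the stated error rate, this should be corrected before any interim data are examined.

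**What to change.** In Section 9.1, state the interim endpoint and the event from which the year is counted, and then adopt one of the following.

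(a) State that the interim cannot support an efficacy claim or an efficacy stop, and keep the final test at two-sided 0.05. This costs no power. It gives up any early efficacy claim.

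(b) Allow an early efficacy claim only at two-sided p < 0.001, with the final test at 0.049. The overall error is 4.9 to 5.0% and the cost is about 0.3 power points. The gain is small: if the true difference is 1.2 mm, the chance of an early claim is about 2% at 11 per arm and 3% at 14 per arm.

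Option (a) is the simpler choice, given how little information an early look would carry. It would also help to say who sees the between-arm results, although this does not change the error rate. Either option needs a short amendment, with the committee and board approvals that Section 10.4 requires. Neither changes the sample size or study procedures.
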